## **8.5 PACKAGING AND LABELING**

Packaging will be undertaken in accordance with the administration schedule. The content of the labeling is in accordance with the local regulatory specifications and requirements.

The appropriate number of packages will be dispensed to cover up to the next dispensing visit (please refer to Section 1.2). Storage conditions and use-by-end date are part of the label text.

Treatment labels will indicate the treatment number (used for treatment allocation and reported in the e-CRF).

## **8.6 STORAGE CONDITIONS AND SHELF LIFE**

Investigators or other authorized persons (eg, pharmacists) are responsible for storing the IMP in a secure and safe place in accordance with local regulations, labeling specifications, policies, and procedures.

Control of IMP storage conditions, especially control of temperature and instructions for handling the Sanofi compound, should be managed according to the rules provided by the Sponsor.

The expiry date and storage conditions are written on the IMP labels. The IMP should be stored between +15°C and +30°C (59°F and 86°F) (Table 1).

## **8.7 RESPONSIBILITIES**

The Investigator, the hospital pharmacist, or other personnel allowed to store and dispense the IMP will be responsible for ensuring that the IMP used in the clinical trial is securely maintained as specified by the Sponsor and in accordance with applicable regulatory requirements.

All IMPs will be dispensed in accordance with the Investigator's prescription and it is the Investigator's responsibility to ensure that an accurate record of IMP issued and returned is maintained.

Any quality issue noticed with the receipt or use of an IMP (deficiency in condition, appearance, pertaining documentation, labeling, expiration date, etc) should be promptly notified to the Sponsor. Some deficiencies may be recorded through a complaint procedure.

A potential defect in the quality of IMP may be subject to initiation of a recall procedure by the Sponsor. In this case, the Investigator will be responsible for promptly addressing any request made by the Sponsor, in order to recall the IMP and eliminate potential hazards.

Under no circumstances will the Investigator supply IMP to a third party (except for direct-to-patient shipment, for which a courier company has been approved by the Sponsor), allow the IMP to be used other than as directed by this clinical trial protocol, or dispose of IMP in any other manner.

### **8.7.1 Treatment accountability and compliance**

Accounting and compliance for IMPs will be performed at Visit 3 and all subsequent on-site visits (excluding telephone visits).

The Investigator will check the compliance to the IMP dose schedule based on the patient diary and will then complete the appropriate site treatment and patient treatment log forms. A visual check on returned IMP will be performed by site staff. In addition, the dosing information will be recorded on the appropriate pages of the e-CRF.

For other NIMP (eg, metformin), the name, start and end date of treatment, total daily dose, etc will be documented in the source documents. Compliance to metformin will be checked by interviewing the patient and reviewing the patient diary at each visit, and documented in the source documents and e-CRF.

Rescue therapy (see Section 8.2.2) is to be reported in the e-CRF. This information should include specific drug name, dose, route of administration, and frequency.

If compliance is inadequate as determined by the Principal Investigator (PI), patients will be trained again and mentored. If sub-optimal compliance continues after training and mentoring, patients may be discontinued at the discretion of the PI after discussion with the Sponsor's/CRO's medical monitor.

### **8.7.2 Return and/or destruction of treatments**

Patients are to return all IMP (unused, in-use, or empty wallets[s]) at each on-site visit (or at final assessment visit in case of permanent premature discontinuation), as described in Section 1.2. IMP accounting is not required at telephone visits.

All used, partially-used, or unused IMPs will be retrieved by the CRO or Delegate. A detailed site and patient treatment log of the returned IMP will be established with the Investigator (or the pharmacist) and countersigned by the Investigator and the monitoring team.

For NIMP not provided by the Sponsor (ie, metformin and rescue therapy), tracking and reconciliation is to be undertaken by the Investigator (or pharmacist if appropriate) according to the system proposed by the CRO.

## 8.8 CONCOMITANT MEDICATION

A concomitant medication is any treatment received by the patient concomitantly to any IMP. The IMP includes sotagliflozin and matching placebo, and glimepiride and matching placebo.

All concomitant medications should be documented on the medications page of the e-CRF. This includes all NIMP treatments that are taken by the patients at any time during the clinical trial, beginning at Visit 1.

Additionally, all medications taken in the 3 months prior to Visit 1, and prior use of SGLT2 inhibitors should be reported.

### 8.8.1 Prohibited prior and concomitant medications

During the study, the following medications are prohibited:

- Initiation of any antidiabetic agents, including oral or injectable antihyperglycemic agents other than the IMP and metformin are not allowed before the rescue therapy. The existing background medication (NIMP) should not be modified before the rescue.
- SGLT2 inhibitors (eg, canagliflozin, dapagliflozin, or empagliflozin), and sulfonylurea are not allowed for rescue.
- Systemic use of glucocorticoids for more than 10 consecutive days (topical, ophthalmic, intra-articular, nasal spray or inhaled applications are allowed).
- IMPs in any other clinical trial.
- Modification of antihypertensive medication before Week 12 is not allowed unless for safety reasons.
- Initiation of any weight loss drugs (eg, phentermine, orlistat).

Patients taking sotagliflozin with concomitant digoxin should have digoxin concentrations monitored and doses reduced as needed. In addition, other P-gp substrates may be affected and the labels of P-gp substrate drugs should be consulted with regards to monitoring and dose adjustments.

**Note:** short term use (<10 consecutive days) of the prohibited medication eg, short-acting insulin for treatment of acute illness or surgery is allowed.

Other medications which are unlikely to interfere with the PK or PD of the IMP or confound interpretation of the study endpoints are allowed as needed and following discussion between the Investigator and the Sponsor/CRO. However, doses of chronically administered medicines should be kept fixed during the trial if at all possible.

The dose of all antihypertensive agents should be kept constant during the 12 weeks following randomization and no antihypertensive agents should be added or withdrawn for the 12 weeks following randomization unless it is considered necessary for safety reasons.

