### 8.1.2 Starting dose and dose adjustment

All patients will receive treatment at a fixed dose of sotagliflozin (or matching placebo) as assigned at randomization throughout the 52-week study period.

All patients will receive glimepiride (or glimepiride-matching placebo) on Day 1 starting from 1 mg daily. Glimepiride (or glimepiride-matching placebo) will be titrated (or mock-titrated) up to 6 mg (or maximum tolerated dose). Titration will be possible at 5 dose levels (1, 2, 3, 4, and 6 mg) through a combination of glimepiride (or matching placebo) capsules with different dose strengths. Table 2 provides an overview of the glimepiride dose levels.

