In case of recurrent hypoglycemia, down-titration of glimepiride (or matching placebo) can be performed at any time during the study for the patients taking a daily dose higher than 2 mg of glimepiride. In the glimepiride blister delivered to the patient, the first column will correspond to the lower dose strength. If an unscheduled phone visit is prompted due to recurrent hypoglycemia, the Investigator may use discretion to advise patients to temporarily (<7 days) decrease glimepiride/matching placebo dose by omitting the capsule of lower dose until they are able to return to the site to be evaluated and receive a new treatment kit as needed. In this case, an on-site visit should occur as soon as possible within 7 days.

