## **8.3 BLINDING PROCEDURES**

### **8.3.1 Methods of blinding**

To maintain blinding, sotagliflozin and placebo tablets, glimepiride and placebo capsules, and their packaging will be blinded. Sotagliflozin versus sotagliflozin-matching placebo and glimepiride versus glimepiride-matching placebo will be indistinguishable.

During the double-blind Treatment Period each treatment package will be labeled with a number, which is generated by a computer program from Sanofi. Investigators will not have access to the randomization (treatment) code except under circumstances described in Section 8.3.2.

The randomization and the treatment allocation will be performed centrally by an IRT. The study biostatistician provides the randomization scheme to the IRT. Then, the IRT will generate the patient randomization list from which is allocates treatment groups to the patients.

Fasting glucose (plasma or serum) and HbA1c will be masked to study sites and patients after randomization and until study end. Additionally, the central laboratory urinalysis by dipstick will not include the measurement of urine glucose.

The CEC members will perform adjudication in a blinded manner.

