### 8.3.2 Randomization code breaking during the study

In case of an AE, the code should only be broken in circumstances when knowledge of the IMP is required for treating the patient.

Code breaking can be performed at any time by using the proper module of the IRT and/or by calling any other phone number provided by the Sponsor for that purpose. If the blind is broken, the Investigator should document the date, time of day, and reason for code breaking. The identity of the unblinded personnel, how the code was broken, and the treatment kit number should also be recorded. The Sponsor should also be informed if the code is broken by the Investigator (or other medical doctor in an emergency situation), the patient must be withdrawn from IMP.

Refer to Section 10.5 for suspected unexpected serious adverse drug reaction (SUSAR) unblinding by the Sponsor.

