## 11 STATISTICAL CONSIDERATIONS

### 11.1 DETERMINATION OF SAMPLE SIZE

The sample size/power calculations were performed based on the primary endpoint of the change of HbA1c from Baseline to Week 52 in the intent-to-treat (ITT) population. Assuming a common standard deviation (SD) of 1.1%, and the true difference between sotagliflozin 400 mg and glimepiride is zero, 310 patients in the sotagliflozin 400 mg and glimepiride groups will ensure that the upper bound of the 2-sided 95% confidence interval (CI) of the adjusted mean difference is below 0.3% with at least 90% power. This sample size will have 80% power to test the non-inferiority of the change of HbA1c from Baseline to Week 52 in completers, with 30% dropout rate.

A sample size of 310 patients in sotagliflozin 400 mg group and 155 patients in placebo group will have >99% power to detect a treatment difference of 0.6% in mean HbA1c change from Baseline to Week 26 between sotagliflozin 400 mg and placebo (SD 1.2%; 2-sided 5% significance level).

A sample size of 155 patients in sotagliflozin 200 mg group and 155 patients in placebo group will have 95% power to detect a treatment difference of 0.5% in mean HbA1c change from Baseline to Week 26 between sotagliflozin 200 mg and placebo (SD 1.2%; 2-sided 5% significance level).

The total sample size will be 930 patients to be randomized (sotagliflozin 400 mg group: 310; sotagliflozin 200 mg group: 155; glimepiride: 310; placebo: 155).

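### The digoxin monitoring rule in Protocol 8.8.1 depends on a treatment assignment that blinded sites cannot know

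*Protocol*

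**What the plan says.** Protocol 8.8.1 states, after its list of prohibited medications: "Patients taking sotagliflozin with concomitant digoxin should have digoxin concentrations monitored and doses reduced as needed". SAP 2.1.2.2 repeats the sentence. The reason is in Protocol 4.2: an interaction study with digoxin found sotagliflozin to be a weak P-gp inhibitor.

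The next sentence of 8.8.1 sends the reader to the labels of other P-gp substrates and is not tied to any arm. Later in the section, sites are asked to hold long-term medicines at a constant dose if they can.

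On the blind, Protocol 8.3.1 says: "Sotagliflozin versus sotagliflozin-matching placebo and glimepiride versus glimepiride-matching placebo will be indistinguishable". Investigators have no access to the code outside 8.3.2, which says: "In case of an AE, the code should only be broken in circumstances when knowledge of the IMP is required for treating the patient". If the code is broken, "the patient must be withdrawn from IMP".

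**The concern.** A monitoring rule is useful only if the person applying it can tell whether its condition is met. Here the condition is that the patient is taking sotagliflozin, which is exactly what the blind conceals. A site that reads the sentence as written cannot decide whether it applies to the digoxin user in front of it.

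What is at stake is the safety of a small and uncounted group: patients whose digoxin level might rise on sotagliflozin and who might not have it checked. A site that is unsure whether the exception applies also meets the general request to leave long-term doses alone, which points the other way.

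**Working it through.** No figure in the plan is in dispute, so the check is mainly a reading of the relevant sections side by side.

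1. **Can a digoxin user be randomized?** Yes. None of the inclusion criteria (7.1) or exclusion criteria E01 to E39 (7.2.1 to 7.2.5) names digoxin. E05 excludes patients likely to need a drug that the protocol does not permit, but digoxin is not on the prohibited list in 8.8.1.

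2. **Can the site tell whether the condition is met?** No. During run-in every patient takes placebo (6.1.1.2), so the condition is false for all. During the 52 treatment weeks the assignment is masked (8.3.1). After the end of treatment sotagliflozin is not supplied (8.9). The condition can therefore be true only while the site is blinded.

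3. **Can the site find out?** Not for this purpose. Section 8.3.2 ties code breaking to an adverse event in which knowing the product is needed for treatment, and a routine drug-level check is not that. Suspected digoxin toxicity might qualify, but only after the event that monitoring is meant to prevent, and the patient would then stop study treatment.

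4. **Do the odds help?** No. Section 11.1 gives the planned numbers: "sotagliflozin 400 mg group: 310; sotagliflozin 200 mg group: 155; glimepiride: 310; placebo: 155".
   - On sotagliflozin: (310 + 155) / 930 = 465 / 930 = 50%.
   - On glimepiride or placebo: (310 + 155) / 930 = 465 / 930 = 50%.

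5. **Does other text close the gap?** Not expressly. Digoxin concentration is in neither the safety laboratory table (Table 3) nor the flow chart (1.2). The P-gp sentence concerns substrates other than digoxin. No section tells sites to treat every digoxin user as if on sotagliflozin.

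6. **Does the protocol write such rules differently elsewhere?** Yes. In 8.1.2, "down-titration of glimepiride (or matching placebo) can be performed at any time during the study" covers active drug and placebo together, and mock titration extends the dosing steps to all arms. Appendix B cites volume depletion with SGLT2 inhibitors and then directs its hydration advice to all patients. The digoxin sentence lacks this extension.

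**The case against.** The strongest reply is that no sensible site would be stuck. Under a double blind every randomized patient may be on sotagliflozin, so the natural reading is to monitor all digoxin users, and that needs no code break. The site will know who they are: "All concomitant medications should be documented on the medications page of the e-CRF". Section 10.1 allows optional visits at any time. Dose reduction follows the measured level, so the arm is not needed in order to act. The adjacent P-gp sentence, which is not tied to an arm, makes a narrow reading less likely. The inhibition is described as weak, and the investigator brochure, to which Protocol 4.2 refers for more safety information, may contain the wider instruction.

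Most of this stands, and it limits the weight of the point. A reader might go further and infer that the rule is unworkable, or that digoxin users on sotagliflozin will go unmonitored. The documents do not support that: nothing prevents a site from checking every digoxin user, and many probably would.

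It might also be said that the protocol often names sotagliflozin in advice given under the blind, as in 8.9 on blood pressure. There, however, the drug is the reason for the advice, and the advice itself is for patients with hypertension. In the digoxin sentence the drug is the condition. The sensible reading is therefore something a site has to supply.

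**Conclusion.** The point holds as a minor patient-safety defect in a stated rule. Digoxin users may enter, the rule written for them depends on a masked fact, and code breaking is not open for routine monitoring.

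Its clinical size cannot be given. The number of digoxin users is not in the documents, nor is the size of the rise in digoxin level. The 50% is only the planned allocation and is not a measure of harm. There is no effect on type I error, power or any efficacy analysis, and none should be inferred.

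The conclusion rests on the protocol and SAP alone. If the investigator brochure or site manuals already tell sites to monitor every digoxin user, the gap is confined to the protocol's wording.

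**What to change.** Replace the digoxin sentence in Protocol 8.8.1 with wording such as: *Any randomized patient who takes digoxin, whatever the treatment arm, is to have the digoxin level monitored and the digoxin dose lowered if the measured level calls for it, without breaking the blind.*

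This makes the rule one that a site can follow, and it states plainly that a digoxin dose may change despite the general request for constant doses. The P-gp sentence can stay as it is. No fixed sampling schedule is needed to cure this defect, and neither is a change to SAP 2.1.2.2, because the SAP does not direct patient care.

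The cost is one sentence and digoxin levels for digoxin users only. In expectation 465/930, or about half, of those monitored would be on glimepiride or placebo and would not need the check. SAP section 4 records database lock on 12 September 2019, so the correction now concerns the plan as written and any later protocol that reuses the sentence.

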### **8.8.2 Concomitant diabetes therapy**

For patients in both groups, background NIMP metformin should be stable throughout the study unless down-titration is required for safety reasons.

The rescue medication(s) that will be used to treat hyperglycemia when a patient's hyperglycemia reaches the rescue threshold are also defined as NIMPs. Rescue medication can be added up to the Investigator's decision except for SGLT2 inhibitors and sulfonylurea. The regimen of the rescue medications will be in accordance with local standard of care and prescribing practice.

### **8.9 POST-STUDY TREATMENT**

Because sotagliflozin may reduce BP, adjustment of antihypertensive medication may be needed during the study in patients with hypertension. Conversely, monitoring for an increase in BP should be performed after withdrawal of study medication. If the BP is elevated after withdrawal of study treatment, the Investigator should consider adding or adjusting antihypertensive medication.

Sotagliflozin and glimepiride will not be provided after EOT. Patient's further treatment for diabetes and other pathologies will be at the Investigator's discretion based on his/her clinical judgment.

## **9 ASSESSMENT OF INVESTIGATIONAL MEDICINAL PRODUCT**

### **9.1 EFFICACY ENDPOINTS**

The methods of assessment of efficacy endpoints are detailed in Section 9.1.5.

#### **9.1.1 Primary efficacy (sotagliflozin 400 mg dose)**

- Change from Baseline to Week 52 in HbA1c (%)

#### **9.1.2 Secondary efficacy endpoints (sotagliflozin 400 mg dose)**

- Change from Baseline to Week 26 in HbA1c
- Change from Baseline to Weeks 26 and 52 in body weight
- Change from Baseline to Week 12 in SBP for patients with baseline SBP  $\geq 130$  mmHg
- Change from Baseline to Week 12 in SBP for all patients
- Proportion of patients with at least 1 documented symptomatic hypoglycemic event ( $\leq 70$  mg/dL) during the 52-week Treatment Period

#### **9.1.3 Secondary efficacy endpoints (sotagliflozin 200 mg dose)**

- Change from Baseline to Weeks 26 and 52 in HbA1c

#### **9.1.4 Other efficacy endpoints (sotagliflozin 400 mg and 200 mg doses)**

- Change from Baseline to Weeks 26 and 52 in FPG
- Number of hospital visits due to hypoglycemia during the 52-week Treatment Period
- Change from Baseline in eGFR
- Change from Baseline to Week 26 and 52 in SBP for all patients and the subset with baseline SBP  $\geq 130$  mmHg
- Change from Baseline to Weeks 12, 26, and 52 in SBP for patients with baseline SBP  $< 130$  mmHg
- Change from Baseline to Weeks 12, 26, and 52 in DBP for all patients and the subset with baseline DBP  $\geq 80$  mmHg
- Proportion of patients requiring rescue treatment for hyperglycemia during the 52-week Treatment Period
- The proportion of patients with HbA1c  $< 6.5\%$ ,  $< 7.0\%$  at Week 52
- The proportion of patients with HbA1c  $< 6.5\%$ ,  $< 7.0\%$  at Week 52 and no documented symptomatic hypoglycemic event ( $\leq 70$  mg/dL) during the 52-week Treatment Period

- PQAT at Weeks 26 and 52

## **9.1.5 Assessment methods of efficacy endpoints**

### **9.1.5.1 Hemoglobin A1c**

Hemoglobin A1c will be assessed at Screening (Visit 1), Baseline (Visit 3), Week 12 (Visit 7), Week 26 (Visit 10), Week 39 (Visit 11), and Week 52 (Visit 12).

For the eligibility and efficacy assessments of the study, HbA1c is measured by a certified Level I “National Glycohemoglobin Standardization Program” central laboratory.

### **9.1.5.2 Body weight measurement**

Body weight is measured at all on-site visits.

Body weight should be obtained with the patient wearing undergarments or very light clothing and no shoes, and with an empty bladder. The same scale should be used throughout the study and calibrated on a regular basis as recommended by the manufacturer. The use of balance scales is recommended; if digital scales are used, testing with standard weights is of particular importance. The floor surface on which the scale rests must be hard and should not be carpeted or covered with other soft material. The scale should be balanced with both weights at zero and the balance bar aligned. The patient should stand in the center of the platform as standing off-center may affect measurement. The weights are moved until the beam balances (the arrows are aligned). The weight is read and recorded in the e-CRF and Source Data. Self-reported weights are not acceptable; patients must not read the scales themselves.

### **9.1.5.3 Fasting plasma glucose measurement**

Plasma glucose is measured in the fasting state at Screening (Visit 1) and all on-site visits, with the exception of Week 2 (Visit 4), during the Treatment Period. Fasting plasma glucose will be performed on the morning of the visit. For the eligibility and efficacy assessments of the study, FPG is measured at a central laboratory.

